The primary endpoint of this study will be to determine if therapy with oral divided-dose ACZ administered each day for week-long period results in at least 15% increase in CBF. Studies have shown between 10% - 15% decrease in cerebral perfusion in patients with relapsing MS (Adhya et al., 2006). Therefore, increases in CBF of at least 15% might result in change to lesion evolution. Baseline CBF measures will be compared to measures obtained at each dose escalation step using paired *t* test and Mann-Whitney test.

Determine the effect of long-term oral ACZ on lesion evolution. The key secondary endpoint of this study is to determine if long-term use of oral daily divided-dose with ACZ improves tissue integrity in a proportion of MS lesions.

MRI scans will be segmented using into white and gray matter, T2 and T1 lesion components and contrast-enhancing lesion component. Expert raters (I.V., S.D., L.F.), who are blinded to treatment arm (see section 6.1) will perform quality control of the automated segmentation and obtain quantitative measures of cerebral perfusion. The number and volume of T2 hyperintense and T1 hypointense lesion will be determined using MRIAP. The ratio of T1 hypointense/T2 hyperintense lesion will be determined for baseline and each crossover period and correlated with CBF, CBV and MTT measures obtained at similar times using the Spearman rank correlation.

Diffusion tensor imaging (DTI) is a reliable, validated technique that quantitatively measures molecular diffusivity within tissue and provides information about its microstructural integrity. DTI will be used to monitor tissue integrity and correlate change with increases in CBF following ACZ.

Tertiary Objectives

Several studies have quantitated transverse and longitudinal relaxation times within lesions and normal-appearing white matter and gray matter. These studies have shown that changes in both transverse and longitudinal relaxation can precede lesion formation and possibly better evaluate lesion evolution as compared to black hole volumes (Papadopoulos et al., 2010; van Walderveen et al., 1999a; Walsh et al., 2014; Warntjes et al., 2013). We will manually delineate regions of interest within lesions to obtain T2 and T1 relaxometry metrics. Lesions within areas with greatest change in CBF will be compared with those with least change. We anticipate a correlation between relaxometry measures and areas with varying CBF.

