- 16. Positive pregnancy test or inability or unwillingness to use effective means of birth control. Effective birth control is defined as:
 - Refraining from all acts of vaginal intercourse (abstinence)
 - Consistent use of birth control pills
 - Tubal sterilization or male partner who has undergone vasectomy
 - Placement of an IUD (intrauterine device)
 - Use, with every act of intercourse, of a diaphragm with contraceptive jelly and/or condoms with contraceptive foam
- 17. Presence of metallic objects implanted in the body that would preclude the ability of the subject to safely have MRI exams.
- 18. Psychiatric illness, mental deficiency, or cognitive dysfunction making compliance with treatment or informed consent impossible.

Withdrawal Criteria

Patients can be withdrawn at any time if the investigator concludes that it would be in the patients' best interest for any reason. Patients may voluntarily withdraw from the study for any reason at any time. They may be considered withdrawn if they state an intention to withdraw, or fail to return for visits, or become lost to follow up for any other reason. Protocol violations should not lead to patient withdrawal unless they indicate a significant risk to the patient's safety. If premature patient withdrawal occurs for any reason, the principle investigator must determine the primary reason for a patient's premature withdrawal from the study and record this information on the Unanticipated Problems Tracking Log.

For patients who are lost to follow-up (i.e., those patients whose status is unclear because they fail to appear for study visits without stating an intention to withdrawal), the investigator will show "due diligence" by documenting in the source documents steps taken to contact the patient, e.g., dates of telephone calls, registered letters, etc. In the case of death, a patient will be considered withdrawn.

Subject Replacement

Patients who prematurely withdraw will not be replaced.

TRIAL SCHEDULE

Visit Schedule:

Stage 1a – IV ACZ in MS Subjects											
Total of 10 subjects (5 healthy and 5 MS patients)											
	Day -7	0 min	15 min	30 min	120 min	240 min					
	Screen										
Treatment		1 gm	1 gm IV bolus ACZ administered								
		immedia									
H&P	Х										
CBC, CMP	Х										
Urine pregnancy	Х										
pCASL MRI		Х	Х	Х	Х	Х					
DSC MRI						Х					

Stage 1b –Oral ACZ dose-escalation in MS Subjects											
Up to a Total of 10 subjects											

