Stage 1b - Participants in this stage of the study will be given escalating divided doses of oral ACZ up to 4000 mg per day to determine both the magnitude of change to cerebral perfusion with maintenance daily oral ACZ therapy and to define the optimum dose(s) for additional studies. Stage 1b and 2 of the study will utilize extended release oral ACZ, distributed by Hermann Research pharmacy and self-administered by the subject.

r	500mg BID	1000 mg BID	1500 mg BID	2000 mg BID	_	Legend + MPL pCASI
W -1	w o	W 2	W 4	W 6	W 8	+ MSFC + EDSS
Screening	+	÷	+	+	+	
	±	‡	+ *	+ +	+ *	

Treatment and data collection for stage 1b will take 2.5 months for each enrolled subject. As many as two subjects can be evaluated during the month and we would anticipate that this portion of the study can be completed within twelve months.

Image analysis will be performed once each subject completes treatment. Cerebral perfusion measures will be determined for each dose by the same unblinded analyst (S.D.).

Stage 2a - This stage will continue to gather information about whether daily oral ACZ is tolerated and the kinetics of the treatment effect. Patients continue on the same dose for 12 consecutive weeks and undergo repeat imaging at predetermined intervals. Sustained treatment over a short duration will allow us to rapidly determine whether sustained treatment with ACZ can alter cerebral blood flow and will provide a go/no-go for future studies using this drug/paradigm. Patients will obtain MRI scans and clinical evaluations every 6 weeks with contrast-based scans repeated at 12 weeks.

Stage 2b - This stage will determine long-term tolerability and if tachyphylaxis is present with oral ACZ. Patients will continue on the same dose for 24 consecutive weeks and undergo repeat imaging at predetermined intervals. MRI scans and clinical evaluations will be obtained every 6

weeks with contrast-based scans repeated every 12 weeks.

Stage 3 - This stage is a prospective delayed-start design to evaluate the potential for ACZ to persistently enhance cerebral perfusion and impact the evolution of MS lesions. This pilot study is anticipated to lead to a larger randomized phase 3 clinical trial.

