The MRI-Analysis Center (MRI-AC), directed by [name], has extensive experience with the management of large amounts of de-identified patient related data and images gathered for both local research studies and national and international studies on thousands of subjects, each with multiple sessions. All data is stored on the MRI-AC macpdbs1 server physically secured in the University Professional Tower Data Center located within virtual Zone 100 (contains servers with protected health information as well as other sensitive or critical data; no access may be initiated directly from the Internet to Zone 100; all servers in Zone 100 are geographically located in secure areas). All workstations physically located in the MRI-AC are confined to Zone 40 (contains the bulk of the computing resources geographically distributed throughout the UTHSCH campus; no access may be initiated directly from the Internet into Zone 40; protected health information must be encrypted; rules for traffic initiated form Zone 40 to other areas: Internet is allowed, Zone 20 is allowed, Zone 100 is restricted to defined servers and protocols). Only individuals who can authenticate to the VPN appliance connected to Zone 40 and have appropriate authorization privileges may access MRI-AC resources from the Internet. Port configurations of the firewalls separating the Zones are managed by the UTHSCH Information Security Staff. Port configuration is managed by a firewall database in accordance with firewall policies and procedures. The MRI-AC Director is the information owner of the macpdbs1 server and the workstations. The steward of the macpdbs1 server is the Data Center Operations and Services (DCOS) division of the UTHSCH Information Technology Department. The steward of the MRI-AC workstations is the Medical School Information Technology (MSIT) Office. We will utilize these resources to manage and store all data and digital images generated as part of this project.

SAMPLE SIZE AND STATISTICAL METHODS

Studies have shown between 10% - 15% decrease in cerebral perfusion in patients with relapsing MS *(Adhya et al., 2006)*. Therefore, increases in CBF of at least 15% might result in change to lesion evolution.

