The primary aim of the proposed study is to evaluate the change in global CBF with ACZ, so the primary outcome is the change in global CBF after 24 weeks relative to pre-treatment baseline. Based on the preliminary data, we expect to see a 15% difference between the ACZ treatment and placebo groups on the improvement in global cerebral perfusion with standard deviation (SD) of 30%. We ran Monte Carlo simulations under a linear mixed effect model (same model as planned for analysis) and calculated a needed total sample size of n=50 to detect a group difference of 0.5 SD at the 24 weeks (phase 1) assuming a within-subject correlation of 0.5, a significance level of 0.05, and 90% power. We hypothesize a similar group difference in phase 2 (ACZ-ACZ group would not change between weeks 24 and 48 but delayed-start group would improve) and similar power to detect this effect. With 50 patients, for Aim 1.2, we will have 80% power to detect an average correlation as low as 0.39 between CBF and MD or FA. Considering a dropout rate of 18%, we need to recruit 60 participants. Aims 2 are mainly exploratory and parameters derived from this study will be used to help design future larger scale confirmatory studies.

All analyses will be intent-to-treat. To summarize the data, descriptive statistics will be used. Demographics and baseline characteristics at randomization will be summarized for each treatment arm. Generalized linear mixed models will be used to analyze all outcomes and will include treatment group and time, group-by-time interaction, and disease duration (stratifying variable) as covariates, and a random intercept to account for within-patient correlation.

For the primary outcome, we will focus on comparing the treatment groups in phase 1. A linear mixed model will be used to compare the estimated change in global CBF between baseline and week 24 in the ACZ and delayed-start groups. A secondary analysis will study ACZ treatment effect on CBF in different regions by treating regions as clusters in the linear mixed model. If normality of CBF outcome does not hold, an appropriate transformation or different outcome distribution will be used.

For the secondary endpoint at 48 weeks (phase 2), a similar mixed model will be used to compare changes in global CBF between weeks 24 and 48 weeks in the early-start and delayed-start groups. The model will include the same terms as for phase 1.

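### Section 2.2 asks whether each oral dose step raises CBF by at least 15%, but the stated tests compare each step only with no change, and one of them ignores the pairing

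*Combined protocol and SAP*

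**What the plan says.** Section 2.2 (Primary & Key Secondary Objective) gives the primary endpoint as whether oral divided-dose ACZ "administered each day for week-long period results in at least 15% increase in CBF". It justifies the threshold on the ground that "increases in CBF of at least 15% might result in change to lesion evolution", and Section 11 repeats that rationale. The analysis follows in the same paragraph: "Baseline CBF measures will be compared to measures obtained at each dose escalation step", by paired t test and Mann-Whitney test. The reference to dose-escalation steps ties this to Stage 1b.

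The Section 4 schedule for Stage 1b reads "Up to a Total of 10 subjects". The Study Design section says the stage is meant "to define the optimum dose(s) for additional studies". Under Subject Replacement, "Patients who prematurely withdraw will not be replaced".

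The 15% figure appears twice more in Section 11. It is the expected between-group difference in the Stage 3 power calculation, where the outcome is described differently ("so the primary outcome is the change in global CBF after 24 weeks relative to pre-treatment baseline"). It is also the cut that sorts brain regions in the MD and FA models. Neither use is a test of the dose-step endpoint. Nowhere do the documents set a null of 15%, a confidence-limit rule, a point-estimate rule or a responder definition for the dose steps.

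**The concern.** The endpoint and the test answer different questions. The endpoint is about a rise of at least 15%, chosen because the protocol regards that size as possibly relevant to lesions. The tests ask whether CBF changed at all. A report that the endpoint was met because p<0.05 would claim a threshold effect that was never tested. A report that it was not met because p>0.05 would dismiss a dose whose data may be compatible with 15% or more.

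The Mann-Whitney test adds a smaller fault. Baseline and on-drug scans come from the same patients, and this test compares independent groups. It discards the pairing that the t test uses, and the plan does not say which of the two governs if they disagree.

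**Working it through.** The plan has no power calculation or precision statement for Stage 1b, so there is no figure of its own to reproduce.

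**Inputs**
- n = 10, the Stage 1b maximum in Section 4.
- Two-sided 0.05: assumed. Section 11 states 0.05 for Stage 3 only, without sidedness.
- SD of within-patient percent change: not given for Stage 1b. Range 10% to 30% assumed; the upper end is the Stage 3 planning SD in Section 11, the only SD in the documents.
- The t test is applied to percent change, the scale of the 15% threshold. The plan does not name the scale.

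**Formulas**
- Standard error = SD/√10, and t(0.975, 9) = 2.262.
- Smallest mean rise significant against zero: c = 2.262 × SD/√10.
- Mean at which the lower 95% limit reaches 15%: 15 + c.
- Mean below which the upper 95% limit is under 15%: 15 − c.
- Probability of a significant rise: noncentral t, 9 degrees of freedom, noncentrality = true mean ÷ (SD/√10).

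Example, SD 10%: c = 2.262 × 10/3.162 = 7.2.

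| SD of % change | Significant vs 0% if mean ≥ | 15% shown if mean ≥ | 15% excluded if mean < | P(significant), true rise 10% | P(significant), true rise 15% |
|---|---|---|---|---|---|
| 10% | 7.2% | 22.2% | 7.8% | 0.80 | 0.99 |
| 15% | 10.7% | 25.7% | 4.3% | 0.47 | 0.80 |
| 20% | 14.3% | 29.3% | 0.7% | 0.29 | 0.56 |
| 30% | 21.5% | 36.5% | −6.5% | 0.16 | 0.29 |

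**Reading the table**
- The cut equals 15% when SD = 15 × √10/2.262 = 21.0%. Below that SD, a step can be significant with an observed mean under 15%.
- At SD 30% a significant mean is at least 21.5%, so the point estimate passes 15%. At that cut the 95% CI runs from 0 to about 43% (2 × 21.5). The lower limit stays under 15% until the mean reaches 15 + 21.5 = 36.5%.
- At SD 30% a true rise of exactly 15% is non-significant with probability 1 − 0.29 = 0.71, so a non-significant step says little about 15%.
- Withdrawals are not replaced. With 8 patients the significance cuts at SD 10%, 20% and 30% become 8.4%, 16.7% and 25.1%.

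**The case against.** The strongest reply is that Stage 1b is exploratory and already aims to estimate. The objective asks to what degree ACZ improves perfusion, and the Stage 1b text speaks of the magnitude of change at each dose. On that reading the mean change is estimated and looked at beside 15%, with the paired test as supporting evidence of a real change. This is fair as to intent, but the plan never says how 15% is to be judged. The only analysis attached to the endpoint is the comparison with baseline.

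A second reply is that the lower-limit rule is demanding with 10 patients. If the true rise were 20%, it would be met 29% of the time at SD 10% and 7% at SD 30%. That stands as a cost. It reflects what 10 patients can establish, and testing against zero does not supply the missing information.

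The objection also rules out four stronger readings a reader might reach:
- That Stage 3 shares the fault. It does not. There 15% is the planning difference, and testing zero difference between arms while powering for an expected effect is standard.
- That a dose short of 15% would be carried forward because p<0.05. Section 8 (Rationale for Selection of Dose) rests the choice on tolerability and greatest perfusion effect, not on significance. The Stage 2a go/no-go asks whether sustained treatment alters CBF, which a comparison with no change does address.
- That a dose with a true 10% rise would usually be called positive. The 0.80 probability needs an SD of 10%, a third of the only SD stated; at 30% it is 0.16.
- That every significant step leaves an interval reaching down to zero. This is so only at the exact cut.

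**Conclusion.** The point holds for the Section 2.2 dose-step endpoint in Stage 1b, and only there. The logical gap does not depend on the SD; the form it takes does. Below an SD of about 21% (10 patients, two-sided 0.05), the observed mean itself can be under 15% and still significant. At 30% the shortfall lies in the confidence limit and in the 71% chance of missing a true 15% rise. The sizes rest on an assumed significance level, an assumed range of SD and all 10 patients being analysed. The harm is a wrong or unsupported answer to the stated endpoint, not a mechanical error in dose choice. It is more than missing detail, because the named tests answer a different question and one of them does not fit paired data. It should be corrected.

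**What to change.** In Section 2.2, make the analysis of each dose step the mean within-patient percent change in CBF from baseline with its 95% CI, read against 15%. State the rule in advance:
- a rise of at least 15% is shown only if the lower limit is 15% or more;
- it is excluded if the upper limit is below 15%;
- otherwise it is unresolved.

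Keep the comparison with zero as supportive evidence of any change, using the paired t test and the Wilcoxon signed-rank test on the within-patient changes in place of Mann-Whitney. State the significance level and its sidedness for these tests.

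This needs a change of wording and one interval per step, with no new patients or scans. The drawback is that many steps will be unresolved: at SD 20%, for example, any observed mean from 0.7% up to just under 29.3% falls in that category.

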Subjects will receive 1 gram bolus of IV ACZ and a second scan using pCASL sequences will be obtained within 15 minutes of infusion. Subjects will remain in the MRI gantry and receive a third scan to determine CBF at 30 minutes from time of infusion. Subjects will then be removed from the MRI gantry and allowed a break.

Subjects will again be placed on the MRI gantry and scout, 3DT1 and pCASL sequences obtained within 120 minutes from time of ACZ infusion. Subjects will then be removed from the MRI gantry and allowed a break. A final scan will be performed using the same sequences within 240 minutes from time of ACZ infusion.

Stage 1b:

Screening Visit – Subjects will receive a complete medical and neurological examination. In addition, all subjects will obtain CBC, CMP and, if female, urine pregnancy test.

Visit 1 – Subjects will receive non-contrast MRI brain using sequences previously described to ensure proper orientation and registration (scout, 3DT1), sequences necessary for segmentation using MRIAP (2D dual echo, 2D fluid-attenuated inversion recovery [FLAIR]) and pCASL sequences to determine CBF at baseline. Subjects will begin taking 250 mg oral ACZ twice daily and continue for two weeks. Subjects will be encouraged to call the PI with any adverse events (see sections 2.4b and 7.1.2) while on study drug.

Visit 2 – Prior to dose-escalation, subjects will receive non-contrast MRI brain sequences as described above to measure effect of previous oral daily divided dose of ACZ on CBF. Upon completion of MRI, subjects will begin taking 500 mg oral ACZ twice daily and continue for two weeks. Subjects will be encouraged to call the PI with any adverse events (see sections 2.4b and 7.1.2) while on study drug.

Visit 3 – Prior to dose-escalation, subjects will receive non-contrast MRI brain sequences as described above to measure effect of previous oral daily divided dose of ACZ on CBF. Upon completion of MRI, subjects will begin taking 1000 mg oral ACZ twice daily and continue for two weeks. Subjects will be encouraged to call the PI with any adverse events (see sections 2.4b and 7.1.2) while on study drug.

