In those unusual instances where adequate control is not obtained by the twice-a-day administration of acetazolamide extended-release capsules, the desired control may be established by means of acetazolamide (tablets or parenteral). Use tablets or parenteral in accordance with the more frequent dosage schedules recommended for these dosage forms, such as 250 mg every four hours, or an initial dose of 500 mg followed by 250 mg or 125 mg every four hours, depending on the case in question.

Acute Mountain Sickness:

Dosage is 500 mg to 1000 mg daily, in divided doses using tablets or extended-release capsules as appropriate. In circumstances of rapid ascent, such as in rescue or military operations, the higher dose level of 1000 mg is recommended. It is preferable to initiate dosing 24 to 48 hours before ascent and to continue for 48 hours while at high altitude, or longer as necessary to control symptoms.

HOW SUPPLIED

Acetazolamide Extended-Release Capsules, 500 mg are white to off-white pellets filled in empty hard gelatin capsules with orange opaque cap imprinted with "EP" in black ink and white opaque body imprinted with "107" in black ink and are supplied as follows:

Unit dose packages of 30 (3x10) NDC 68084-401-21

Storage and Drug Accountability

Acetazolamide tablets will be stored at room temperature (between 68°F to 77°F) as suggested by the manufacturer. Intravenous formulation of ACZ will be stored as lyophilized powder at the temperature specified above in the Hermann Research pharmacy. Lyophilized powder will be reconstituted prior to infusion by the pharmacy. All study medication will be stored at the Hermann Research pharmacy and dispensed as needed during study.

TREATMENT

Rationale for Selection of Dose

The ACZ challenge test, using 1000 mg IV ACZ, is a commonly utilized clinical tool in evaluating patients with chronic intracerebral occlusive disease and is a reliable predictor of critically reduced cerebral perfusion (Vagal et al., 2009). Oral doses as high as 4000 mg daily have been previously used in the NORDIC clinical trial (NORDIC Idiopathic Intracranial Hypertension Study Group Writing Committee et al., 2014).

Participants in this study will be treated with the highest tolerated dose of oral ACZ extended release capsules shown to exert the greatest effect on cerebral perfusion. This dose will also be utilized for an anticipated subsequent large phase 3 trial to determine clinical efficacy.

Study Drug Formulations

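### Stage 1b pairs a suitable paired t test with a Mann-Whitney test, which is the wrong rank test for repeated scans of the same patients; Wilcoxon signed-rank should replace it

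*Combined protocol and SAP*

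**What the plan says.** The test is specified in the protocol's Primary & Key Secondary Objective section: "Baseline CBF measures will be compared to measures obtained at each dose escalation step using paired *t* test and Mann-Whitney test". The same paragraph sets the primary endpoint as whether oral acetazolamide "results in at least 15% increase in CBF".

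The Stage 1b text under Study Visits and Procedures shows that these are repeated measurements on the same people. Visit 1 obtains "pCASL sequences to determine CBF at baseline", and each later visit rescans the same subject "to measure effect of previous oral daily divided dose of ACZ on CBF". The Trial Schedule sets the stage size as "Up to a Total of 10 subjects".

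The paragraph does not say which of the two tests is the main one, when the rank test applies, or what follows if they disagree. The section Sample Size and Statistical Methods does not mention the Stage 1b tests and gives no SD, correlation or power for that stage.

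**The concern.** A Mann-Whitney test compares two independent samples. Here the two samples are the same patients at two times. The rank test that corresponds to a paired t test is the Wilcoxon signed-rank test.

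When scans from one patient are positively correlated, the independent-samples test sets the change against between-patient spread that the pairing would have removed. It then rejects too rarely, both when there is no change and when there is one. With at most 10 patients normality is hard to check, so an analyst could well lean on the rank result. The paired t test could then show a rise that the rank test does not, with no rule for settling the conflict.

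There is a smaller, related gap. Both tests ask whether CBF changed at all, while the endpoint beside them asks for a rise of at least 15%. Nothing in the paragraph links the test result to that threshold.

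**Working it through.** The plan gives no power or error rate for Stage 1b, so there is no figure of its own to reproduce. The check asks how much the choice of rank test matters.

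**Inputs.** n = 10 pairs, the Stage 1b maximum in the Trial Schedule. A true rise of 15 percentage points, from the endpoint. Two-sided 5% level (sidedness is not stated; assumed). The only variability figures are those for Stage 3 in Sample Size and Statistical Methods, where the improvement in perfusion is expected "with standard deviation (SD) of 30" per cent and the within-subject correlation is 0.5. Borrowing them for Stage 1b is an assumption, so SDs of 10-30% and correlations of 0-0.9 were examined.

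**Why pairing matters.** With SD σ at each scan and correlation ρ, the mean change over n patients has variance 2σ²(1−ρ)/n. A comparison that treats the scans as independent uses 2σ²/n. Its standard error is too large by a factor 1/√(1−ρ): 1.41 at ρ = 0.5 and 2.24 at ρ = 0.8.

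**Paired t test, exact (noncentral t, 9 df).** SD of change = σ√(2(1−ρ)).
- σ = 30, ρ = 0.5: SD of change = 30 × √1 = 30; 15/30 = 0.5; noncentrality 0.5 × √10 = 1.58; power 29%.
- σ = 15, ρ = 0.5: SD of change 15; 15/15 = 1.0; noncentrality 3.16; power 80%.

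**All three tests, simulated** (20,000 bivariate normal samples per row, exact critical values), power for a 15-point rise:

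| SD | Correlation | Paired t | Signed-rank | Mann-Whitney |
|---|---|---|---|---|
| 30% | 0 | 17% | 16% | 16% |
| 30% | 0.5 | 30% | 28% | 10% |
| 30% | 0.8 | 62% | 60% | 6% |
| 20% | 0.5 | 56% | 54% | 27% |
| 20% | 0.8 | 91% | 90% | 26% |
| 15% | 0.5 | 80% | 78% | about 53% (repeat runs 52-54%) |
| 15% | 0.8 | 99% | 99% | 57% |
| 10% | 0.5 | 99% | 98% | 92% |

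**Size with no true change (SD 30%).** Mann-Whitney rejects in 4.1% of samples at correlation 0, about 0.7-0.9% at 0.5, and about 0.1% or less at 0.8. The paired t and signed-rank tests stay near 5%.

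**Disagreement.** At SD 30% and correlation 0.5, Mann-Whitney misses 68% of the samples in which the paired t test is significant. At correlation 0.8 the two tests disagree in 56% of samples.

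**Reading of the 30%.** It may be meant as the SD of the change, not of each scan. At correlation 0.5 the two readings coincide (30 × √1 = 30). If the SD of change is held at 30 and the correlation raised to 0.8, the paired t test stays at 29% and Mann-Whitney falls to about 1%.

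**The 15% threshold.** Suppose the true mean rise is 8%, well short of 15%. The paired t test against zero is then significant 62% of the time if the SD of change is 10 points, 33% at 15, 20-21% at 20 and 12% at 30. The 8% and these SDs are all assumed. They show only that significance against zero does not answer the endpoint, and that how often the two part company depends on the SD.

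**The case against.** The strongest reply is that the sentence already contains a valid paired analysis, and names it first. That stands. A reader might infer that Stage 1b as a whole ignores the pairing, but the text does not support this: the fault is confined to the companion rank test.

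A reader might also infer that Stage 1b will miss most real CBF rises because of Mann-Whitney. The documents do not support that either. They give no Stage 1b variability, and Mann-Whitney power runs from about 10% to 92% at correlation 0.5 as the SD falls from 30% to 10%. At SD 30% and correlation 0.5 the correct paired tests also miss about 70%, because n is only 10; 80% power for the paired t test would need 34 pairs.

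The error is also conservative, so it creates no false claim of benefit.

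It is tempting to add that a faulty p-value would misdirect the later dose. But Rationale for Selection of Dose speaks of "the highest tolerated dose of oral ACZ extended release capsules shown to exert the greatest effect on cerebral perfusion", that is, tolerability and size of effect. The stated go/no-go belongs to Stage 2a. No text makes a Stage 1b p-value the gate, and none allows a significant rise below 15% to count as meeting the endpoint.

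Finally, the statistics section applies mixed models with a random intercept to all outcomes, which would handle the pairing. That model carries treatment group, a group-by-time interaction and a stratifying variable. It suits the randomised Stage 3, not the single-arm Stage 1b. If it was meant to supersede the objectives paragraph, the two sections need reconciling.

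**Conclusion.** The point holds as a minor correction. Mann-Whitney does not fit the paired Stage 1b scans, while the paired t test beside it does. That conclusion rests on the design alone and needs no assumed figure.

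The size of the loss does depend on assumptions. At correlation 0.5 it is about 18 percentage points of power at SD 30% (28 − 10), 25 at SD 15% (78 − 53) and 6 at SD 10% (98 − 92). It disappears when scans are uncorrelated and widens at SDs of 15-30% as the correlation rises. The practical consequence is that two named tests can give conflicting answers with no rule for which one decides.

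The mismatch between a test of no change and a 15% endpoint is real but is a matter of reporting. The Stage 3 comparison, analysed by mixed model, is unaffected.

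**What to change.** In the Primary & Key Secondary Objective section:

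- Replace the Mann-Whitney test with the Wilcoxon signed-rank test.
- Name the paired t test as the main Stage 1b analysis and the signed-rank test as its check.
- Report the mean percent change in CBF from baseline at each dose step with a 95% confidence interval, and read that interval against 15% as well as against zero.

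While editing, reconcile the number of dose steps, which fixes the number of comparisons: the Trial Schedule shows four dose levels and the Stage 1b visit text five. Also state whether the mixed models in Sample Size and Statistical Methods are meant to cover Stage 1b.

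The cost is one or two sentences for the tests and the interval. No new data, visits or patients are needed.
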